#### 16.4 Translational Studies

We will explore the genomic and transcriptomic landscape of RAIA tumors for signatures that correlate to therapeutic benefit achieved in patients with RAI-avid recurrent and/or metastatic thyroid cancer treated with  $^{131}\text{I}$  in combination with placebo or selumetinib. Exploratory analysis will include correlating response to tumor genotypes. All tumors will be evaluated for common thyroid cancer gene mutations (BRAF, RAS, PIK3CA, AKT, RET/PTC, PAX8/PPAR $\gamma$ ). Descriptive statistics and graphical techniques will be used to summarize this data by treatment arm. Given the small sample size, all these analyses will be considered hypothesis generating and exploratory.

#### 16.5 Total Sample Size

A maximum of 56 evaluable patients (28 per arm) will be accrued onto this randomized phase II study unless the study is closed early for excessive toxicity. We anticipate accruing an additional 5% of patients to account for ineligibility, cancellation, major treatment violation, or other reasons. Therefore, maximum accrual is 60 patients (30 per arm).

#### 16.6 Expected Accrual and Accrual Duration

The expected accrual rate is about 3 patients per month for the ACCRU group. With this accrual rate, we expect to finish accrual within about 20 months, assuming we accrue 60 total patients.

#### 16.7 Anticipated time to study completion

We anticipate that the study will take approximately 3 years to complete. This allows a 6 month follow-up for the final patient enrolled, along with data entry, data clean-up, and analysis.

#### 16.8 Data & Safety Monitoring

The principal investigator(s) and the study statistician will review the study at least twice a year to identify accrual, adverse event, and any endpoint problems that might be developing. The trial is monitored continually by the study team who are notified of every grade 4 and 5 event in real time. The Mayo Clinic Cancer Center (MCCC) Data Safety Monitoring Board (DSMB) is responsible for reviewing accrual and safety data for this trial at least twice a year, based on reports provided by the MCCC Statistical Office.

The stopping rule specified below is based on the knowledge available at study development. We note that the Adverse Event Stopping Rule may be adjusted in the event of either (1) the study re-opening to accrual after any temporary suspension or (2) at any time during the conduct of the trial and in consideration of newly acquired information regarding the adverse event profile of the treatment(s) under investigation. The study team may also choose to suspend accrual because of unexpected adverse event profiles that have not crossed the specified rule below.

Accrual will be temporarily suspended to this study if at any time we observe events considered at least possibly related to study treatment (i.e., an adverse event with attribute specified as "possible", "probable", or "definite") that satisfy any of the following criteria for each arm separately:

- If at any time, 6 of the initial 20 treated patients or 30% or more of all patients (i.e. when accrual is greater than 20 patients) have experienced a grade 4 non-hematologic adverse event.
- If at any time, 2 of the initial 20 treated patients or 10% or more of all patients (i.e. when accrual is greater than 20 patients) have experienced a grade 5 adverse event (non-progressive disease).
- In addition, each grade 5 event will be reviewed on a case by case basis in a real time fashion to determine whether study accrual should be suspended. We may suspend accrual after just 1 grade 5 AE, if needed, for patient safety.

16.9a Accrual Monitoring Stopping Rule

Given the expected accrual rate is around 4 patients per month, it is expected that the study will take around 25 months to fully accrue. We plan to monitor the accrual continually and if we only end up accruing 10 patients or less in the first year (after study activation), we will consider stopping the trial for slow accrual.

16.9b Primary Endpoint Completion Time Estimation (For clinicaltrials.gov reporting):

The primary endpoint is a comparison of the confirmed response rate between the 2 treatment arms, as discussed in detail in section 16.2. The final analysis is expected to take place around 36 months after the study begins, so we expect the primary endpoint completion time to be around 36 months after study activation.

16.9c Inclusion of Women and Minorities

This study will be available to all eligible patients, regardless of race, gender, or ethnic origin. There is no information currently available regarding differential effects of this regimen in subsets defined by race, gender, or ethnicity, and there is no reason to expect such differences to exist. Based on prior studies involving similar disease sites, we expect about 25% of patients will be classified as minorities by race and about 55% of patients to be women. Expected sizes of racial by gender subsets are shown in the following table:

Accrual Targets			
Ethnic Category	Sex/Gender		
	Females	Males	Total
Hispanic or Latino	6	5	11
Not Hispanic or Latino	27	22	49
Ethnic Category: Total of all subjects	33	27	60
Racial Category			
American Indian or Alaskan Native	0	0	0
Asian	2	1	3
Black or African American	6	5	11
Native Hawaiian or other Pacific Islander	1	0	1
White	24	21	45
Racial Category: Total of all subjects	33	27	60

**Ethnic Categories:**

**Hispanic or Latino** – a person of Cuban, Mexican, Puerto Rican, South or Central American, or other Spanish culture or origin, regardless of race. The term “Spanish origin” can also be used in addition to “Hispanic or Latino.”

**Not Hispanic or Latino****Racial Categories:**

**American Indian or Alaskan Native** – a person having origins in any of the original peoples of North, Central, or South America, and who maintains tribal affiliations or community attachment.

**Asian** – a person having origins in any of the original peoples of the Far East, Southeast Asia, or the Indian subcontinent including, for example, Cambodia, China, India, Japan, Korea, Malaysia, Pakistan, the Philippine Islands, Thailand, and Vietnam. (Note: Individuals from the Philippine Islands have been recorded as Pacific Islanders in previous data collection strategies.)

**Black or African American** – a person having origins in any of the black racial groups of Africa. Terms such as “Haitian” or “Negro” can be used in addition to “Black or African American.”

**Native Hawaiian or other Pacific Islander** – a person having origins in any of the original peoples of Hawaii, Guam, Samoa, or other Pacific Islands.

**White** – a person having origins in any of the original peoples of Europe, the Middle East, or North Africa.

## 17.0 Pathology Considerations/Tissue Biospecimens

### 17.1 Tissue Biospecimen Submission

#### 17.11 Summary Table of Tissue Biospecimens for This Protocol

Type of tissue biospecimen to submit	Mandatory or optional	When to submit	Reason for submission (background/methodology section)	Where to find specific details for biospecimen submission
Formalin-fixed paraffin-embedded (FFPE) tissue blocks with corresponding H&E (OR (20) 5 micron- and (10) 10-micron unstained slides with corresponding H&E)	Mandatory	≤60 days after registration	Correlative studies (Section 17.3)	Section 17.2

If an institution is not able to provide the tissue, it does not cause the patient to be ineligible; however, the collection of these tissues is **strongly recommended**.

### 17.2 Paraffin Embedded Tissue Blocks/Slides (mandatory for research tissue)

17.21 Submit one formalin fixed paraffin-embedded (FFPE) tumor tissue block from the primary or recurrent/metastatic thyroid cancer. A corresponding H&E slide from the submitted block must be provided to permit quality assessment (QA) of tissue block.

17.22 The FFPE tissue block is preferred; however, if an institution is unable to provide a tissue block, cut 20 five-micron unstained slides and mount on charged glass slides and 10 ten-micron unstained slides mounted on uncharged slides. **Label the slides with the ACCRU patient ID number, accession number, and order of sections (i.e., 1-11). Do not use sticky labels on the slides. H&E stain the first cut slide (i.e., slide labeled 1).** For samples containing less than 7 square millimeters of tumor tissue, multiple sections should be mounted onto each slide to ensure that the appropriate amount of tumor tissue is available. Ideally, each slide must have a minimum of 75% tumor tissue on the slide to be deemed adequate for study. **Do not bake or place cover slips on the slides.**

17.23 The following materials below are mandatory (unless indicated otherwise) and required for shipment:

- Paraffin embedded tissue blocks with corresponding H&E (or 30 slides per instructions in section 17.22)
- Research Tissue Specimen Submission Form
- Surgical Pathology Report (Do not redact the accession number(s))
- Operative Report-Optional

17.24 Ship all block/slide tissue specimens and accompanying materials to the following:

ACCRU Operations Office  
Attn: PC Office (Study RU241306I)

[REDACTED]

[REDACTED]

[REDACTED]

### 17.3 Study Methodology and Storage Information

17.31 Submitted tissue samples will be analyzed as follows:

17.311 FFPE tumor tissue blocks/ unstained slides will be collected in search of biomarkers that may correlate to clinical responses to either  $^{131}\text{I}$  in combination with placebo or selumetinib. To maximize the information garnered from limited archival tissues, highly sensitive array-based technologies will be used to quantify the gene expression and sequence of cancer genes.

We will isolate RNA from the tissues for interrogation with a custom-designed Nanostring platform for two purposes: a) Detection of fusion oncogenic transcripts (that cannot be detected by an exon-capture method), and b) To measure mRNA levels of three major classes of transcripts: 1) Markers of the MAPK pathway transcriptional output (e.g. Etv1, Etv4, Etv5, Spry2, Spry4, Dusp6); 2) Genes required for thyroid hormone biosynthesis (e.g. Nkx2.1, Pax8, Foxe1, Tg, Tpo, TshR, Nis, Pendrin, Dio2); and 3) Possible determinants of intrinsic resistance to therapy, including adaptive responses to MAPK pathway inhibition that have already been found to be relevant for *BRAF* MUT tumors (i.e. neuregulin mediated activation of HER3 kinase): e.g. Nrg1 (and other RTK ligands), Her2, Her3, TGF $\beta$ R2). The assay will interrogate ~200 transcripts, of which only a few examples of each class are listed above.

Expression of a panel of cytokeratins, among other genes, will be used to standardize for epithelial cell content in the biopsy material.

A portion of the tumor will be processed for DNA extraction using standard laboratory protocols. Approximately 200 ng DNA isolated from archival samples will be analyzed by exon capture-based next generation sequencing of a custom panel of approximately 300 cancer gene exomes or more, which incorporates all known thyroid cancer oncogenes and tumor suppressors. Genomic DNA from the 10 ml blood draw will be used as a germline comparator to aid in identifying tumor specific alterations. According to patient consent information, remaining DNA will be stored frozen at -70°C by BAP. As protocols are developed, they will be presented for ACCRU, IRB, and ITOG review and approval.

Given the fast-paced development of genomic and transcriptomic platforms, it is possible that by the time tissues from this study are available for analysis, more advanced DNA and RNA analytic techniques for FFPE tissues (e.g., whole exome, whole genome, RNAseq, etc.) may be available and preferred over the approach detailed above. If so, the studies discussed

above may be performed on one of these newer platforms to investigate the overall aim of identifying markers that correlate to clinical efficacy.

All analyses of the archival tumor tissue will be performed by [name], Memorial Sloan-Kettering Cancer Center (New York, New York).

- 17.32 At the completion of the study, any unused/remaining material will be stored in the ACCRU Central Operations Office (attn: Pathology Coordinator) for future research according to the patient consent permission. Potential future research may include immunohistochemistry (IHC) analyses, DNA extraction, RNA extraction, and/or tissue microarray (TMA) construction to analyze predictive biomarkers, changes in expression pattern with therapy, and correlation with response and/or adverse events. For TMAs, the donor block remains intact except for 6 small (0.6mm) holes where the cores were taken. This process has minimal impact on the utility of the block for future clinical diagnostic needs. When a protocol is developed, it will be presented for ACCRU, IRB and ITOG review and approval. (These specimens may only be used subsequently for ITOG-approved research protocols.)
- 17.34 The institutional pathologist will be notified by the ACCRU Operations Office (Pathology Coordinator) if the block may be depleted.
- 17.35 Blocks requested to accommodate individual patient management will be returned promptly upon request.

17.4 Return of Genetic Testing Research Results

Because the results generated by the genetic testing included in this section are not currently anticipated to have clinical relevance to the patient or their family members, the genetic results will not be disclosed to the patients or their physicians.

If, at any time, genetic results are obtained that may have clinical relevance, IRB review and approval will be sought regarding the most appropriate manner of disclosure and whether or not validation in a CLIA certified setting will be required. Sharing of research data with individual patients should only occur when data have been validated by multiple studies and testing has been done in CLIA-approved laboratories.

## 18.0 Records and Data Collection Procedures

All data must be entered by Remote Date Entry (RDE) and completed by qualified and authorized personnel. Access the RAVE RDE system through the iMedidata portal at <https://login.imedidata.com>. All data on the CRF must reflect the corresponding source document. Please refer to the ACCRU website for instructions [REDACTED]. NOTE: All reports must be de-identified and labeled with the study number, ACCRU patient ID number and initials.

### 18.1 Submission Timetable

#### Initial Material(s)

CRF	Active-Monitoring Phase (Compliance with Test Schedule Section 4.0)
On-Study	
Baseline Adverse Event	
RECIST Measurement – Baseline	
Research Blood Submission – Baseline (see Section 14.0)	≤2 weeks after registration
Research Tissue Submission - Baseline (see Section 17.0) 	
Endocrine Laboratory - Baseline	
OP and Path Reports (see Section 17.0) 	
End of Active Treatment/Cancel Notification Form	Submit ≤2 weeks after registration if withdrawal/refusal occurs prior to beginning protocol therapy

1. Attach a copy of OP and path reports in RAVE using the Supporting Documentation Form for documentation of disease. This is in addition to the pathology material requirements for tissue submission (Section 17.0).
2. As per Section 17.0, research tissue biospecimen should be submitted ≤ 60 days after registration.

**Test Schedule Material(s)**

CRF	Active-Monitoring Phase (Compliance with Test Schedule Section 4.0)		
	At each evaluation during treatment	At end of treatment	Observation
Evaluation/Treatment	X 	X	
Evaluation/Observation			X
Nadir/Adverse Event	X	X	X 
RECIST Measurement			X 
Endocrine Laboratory			X
RT Material		X	
End of Active Treatment/Cancel Notification		X	
Notification – Grade 4 or 5 Non-AER Reportable Events/Hospitalization	At each occurrence (see Section 10.0)		
ADR/AER	At each occurrence (see Section 10.0)		

1. Attach a copy in RAVE for documentation of response or progression on the Supporting Documentation Form.
2. Complete only at 1 month post I-131 evaluation during Observation (see Section 4.0).
3. Complete at each evaluation during Active Treatment (see Section 4.0).

**Follow-up Material(s)**

CRF	Event Monitoring Phase				
	q. 3 months until PD for the first 12 months post-I  therapy and every 6 months after that 	At PD	After PD q. 6 mos.	Death	New Primary
Event Monitoring 	X	X	X	X	At each occurrence

1. If a patient is still alive 2 years after randomization, no further follow-up is required.
2. Attach a copy in RAVE for documentation of progression on the Supporting Documentation Form.

## 19.0 Budget

### 19.1 Costs charged to patient:

Each site should review the test schedule (Section 4.0) taking into account local and regional coverage policies to determine which items are standard of care and which are research at their site. Refer to the payment synopsis for funding provided per accrual for covering study costs, as well as any additional invoiceables that may be allowed.

## PATIENT'S MEDICATION DIARY

Today's date \_\_\_\_\_  
Patient Name \_\_\_\_\_  
(initials acceptable)

Patient Study ID RU241306I

### INSTRUCTIONS TO THE PATIENT:

1. Complete one form for each 28-day cycle.
2. You will take your dose [ \_\_\_\_\_ mg ( \_\_\_\_\_ 25 mg pills)] TWICE each day (for a total dose of \_\_\_\_\_ mg per day) beginning on Week 1, Day 1 and continued through 2 days after therapeutic  $^{131}\text{I}$  therapy has been administered. It is recommended to take selumetinib (or placebo) on an empty stomach (1 hour before or 2 hours after a meal), approximately 12 hours apart with a glass of water. (NOTE: Avoid excessive sun exposure and use adequate sunscreen protection if sun exposure is anticipated. Do not take vitamin E or multivitamin supplements that provide a total daily dose in excess of 100% of the recommended daily allowance for vitamin E.)
3. Record the date and the time you took them.
4. If you have any comments or notice any side effects, please record them in the Comments column.
5. Bring your pill bottle and this form to your physician when you go for your next appointment.

Date	Day	Time Taken	Comments	Date	Day	Time Taken	Comments
	1				11		
	2				12		
	3				13		
	4				14		
	5				15		
	6				16		
	7				17		
	8				18		
	9				19		
	10				20		

Date	Day	Time Taken	Comments	Date	Day	Time Taken	Comments
	21				26		
	22				27		
	23				28		
	24				29		
	25				30		

Patient's Signature: \_\_\_\_\_ Date: \_\_\_\_\_

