(defined as urinary iodine documented to be <300 mcg/day by either a spot urinary iodine or 24-hour urinary iodine measurement).

3.29d Any of the following because this study involves an investigational agent whose genotoxic, mutagenic and teratogenic effects on the developing fetus and newborn are unknown:

- Pregnant women
- Nursing women
- Men or women of childbearing potential who are unwilling to employ adequate contraception

3.29e Co-morbid systemic illnesses or other severe concurrent disease which, in the judgment of the investigator, would make the patient inappropriate for entry into this study or interfere significantly with the proper assessment of safety and toxicity of the prescribed regimens.

3.29f Immunocompromised patients and patients known to be HIV positive and currently receiving antiretroviral therapy. NOTE: Patients known to be HIV positive, but without clinical evidence of an immunocompromised state, are eligible for this trial.

3.29g Uncontrolled intercurrent illness including, but not limited to, ongoing or active infection, hepatitis B infection, hepatitis C infection, symptomatic congestive heart failure, unstable angina pectoris, cardiac arrhythmia, or psychiatric illness/social situations that would limit compliance with study requirements.

3.29h Receiving any other investigational agent which would be considered as a treatment for the primary neoplasm. (NOTE: Performance of investigational  $^{124}\text{I}$  PET/CT scans is allowed prior to and during conduct of this study.)

3.29i Other active malignancy  $\leq 2$  years prior to registration that will interfere with conduct of this trial. EXCEPTIONS: Non-melanotic skin cancer or carcinoma-in-situ of the cervix. NOTE: If there is a history of prior malignancy, patients must not be receiving other specific treatment (chemotherapy, hormonal therapy, radiation) for their cancer.

3.29j Not willing to discontinue use of supplemental vitamin E.

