Patients of Asian ethnicity are not excluded from studies evaluating Selumetinib. However, when considering enrolling an individual of Asian ethnicity to a Selumetinib clinical study, investigators should make a clinical judgment as to whether the potential risk of experiencing higher Selumetinib plasma levels outweighs the potential benefit of treatment with Selumetinib. The Patient Information and Consent form for studies of Selumetinib includes information on the possibility of higher Selumetinib plasma levels and occurrence of adverse events in Asian subjects than in subjects who are not of Asian origin. Investigators should be aware of the potentially higher risk of adverse events when monitoring patients of Asian ethnicity receiving treatment in clinical studies of Selumetinib.

As reproductive toxicology data indicate that selumetinib has adverse effects on embryofoetal development and survival at dose levels that do not induce maternal toxicity in mice, the following restrictions apply:

Selumetinib/placebo should not be administered to pregnant or breast-feeding women and conception while on treatment must be avoided. Female patients of child-bearing potential will be required to use reliable methods of contraception for the duration of the study and until

4 weeks after the last dose of Selumetinib. Of note, patients may be requested to maintain contraception and avoid pregnancy for a longer period of time after  $^{131}\text{I}$  administration according to institutional guidelines.

Male patients with sexual partners who are pregnant or who could become pregnant (i.e., women of child-bearing potential) should use acceptable methods of contraception for 3 months after the last dose of selumetinib/placebo to avoid pregnancy and/or potential adverse effects on the developing embryo. Of note, patients may be requested to maintain contraception and avoid pregnancy for a longer period of time after  $^{131}\text{I}$  administration according to institutional guidelines.

Selumetinib/placebo capsules contain vitamin E in the form of D- $\alpha$ - Tocopheryl polyethylene glycol 1000 succinate (TPGS), a water-soluble form of vitamin E which acts as a formulation excipient. The maximum daily dose of vitamin E that a study subject may receive from selumetinib/placebo is approximately 261.6 mg/day. Therefore:

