Patients should not take any supplemental vitamin E. High doses of vitamin E have been reported to cause bleeding and interrupt blood coagulation processes.

Selumetinib/placebo should be administered with caution in patients who are also receiving concomitant Coumadin anticoagulant medications, e.g. warfarin. These patients should have their INR monitored/anticoagulation assessments conducted more frequently and the dose of the anticoagulant should be adjusted accordingly.

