15.1 Selumetinib (AZD6244 Koselugo™) or selumetinib-matched placebo

15.11 **Background:** The RAS/RAF/MEK/ERK pathway is an important mediator of many cellular processes including proliferation, survival, differentiation, apoptosis, motility and metabolism. This pathway is often aberrantly activated in human tumors due to the overexpression of activated K-RAS, mutant b-Raf, or other growth factor receptors. Selumetinib is a selective mitogen-activated protein kinase (MEK) inhibitor. By inhibiting MEK, selumetinib inhibits ERK phosphorylation. Thus, selumetinib may inhibit oncogenic growth signaling in tumor cells by targeting the RAS/RAF/MEK/ERK pathway.

15.12 **Formulation:**

The drug product consists of a series of plain, HPMC capsules containing 10 mg (white) and 25 mg (blue) selumetinib (expressed as free-base) for oral administration. Selumetinib capsules are supplied in white, HDPE bottles with desiccant, a tamper evident induction seal membrane and child resistant screw closure.

The 10 mg capsule is presented as either a plain white capsule with a center band, or white to off-white capsule with a center band marked with 'SEL 10' printed in black ink.

The 25 mg capsule is presented as either a plain blue capsule with a center band, or blue capsule with a center band marked with 'SEL 25' printed in black ink.

Apart from the markings, plain and marked capsules are identical in all other aspects.

The capsules contain selumetinib Hyd-Sulfate and Vitamin E polyethylene glycol succinate (also known as TPGS - a water soluble form of vitamin E)Placebo composition is consistent with the composition of drug product, with the absent drug substance being replaced by Vitamin E polyethylene glycol succinate. The same HPMC capsule shells are used for both placebo and active drug products.

Both selumetinib and placebo are supplied in 25 mg capsules in bottles containing 60 capsules each.

15.13 **Preparation and Storage:** Store the selumetinib or placebo capsules in the original packaging until use at room temperature (20° C-25° C). Brief excursions are permitted between 15° C and 30° C. For further information refer to the investigational product label.

15.14 **Administration:** Selumetinib should be taken on an empty stomach, 1 hour before or 2 hours after a meal. Take capsules with water only.

15.15 **Pharmacokinetic information:**  

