#### **Metabolism -**

Cytochrome P450 3A4 is the predominant isoform responsible for selumetinib oxidative metabolism with CYP2C19, CYP1A2, CYP2C9, CYP2E1, and CYP3A5 involved to a lesser extent. Its active metabolite, N-desmethyl selumetinib is approximately 3-5 times more potent than selumetinib, and generated primarily by CYP1A2, CYP2C19, CYP2C9 and CYP2C8 and metabolized through the same routes as selumetinib.

**Special Populations** – Renal impairment is expected to have minimal effect on exposure to selumetinib. Patients with moderate and severe hepatic impairment may experience higher exposures of approximately 1.5-and 3-fold, respectively. It is recommended that investigators take this information into consideration if patient experience moderate or severe hepatic impairment during the study treatment.

15.16 **Potential Drug Interactions:** High vitamin E doses may potentiate the anticoagulant activity of warfarin. Monitor PT/INR more frequently in patients receiving both selumetinib and warfarin.

The concomitant intake of supplemental vitamin E should be avoided in all subjects receiving selumetinib.

Avoid co-administering selumetinib with medicinal products that are strong inhibitors of CYP3A4 (eg, clarithromycin, grapefruit juice, oral ketoconazole) and CYP2C19 (eg, ticlopidine). If co-administration is unavoidable, patients should be carefully monitored for AEs. No dose adjustment is necessary for

use of selumetinib with moderate CYP3A4 or CYP2C19 inhibitors. Patients should be carefully monitored for AEs when co-administered with moderate CYP3A4 or CYP2C19 inhibitors.

Avoid concomitant use of strong CYP3A4 inducers (eg, phenytoin, rifampicin, carbamazepine, St. John's Wort) or moderate CYP3A4 inducers with selumetinib.

Selumetinib may be an inhibitor of OAT3 and the potential for a clinically relevant effect on the PK of concomitantly administered substrates of OAT3 cannot be excluded.

Based on *in vitro* data and SimCYP simulations, selumetinib is considered unlikely to cause clinically significant drug-drug interaction via inhibition or induction of CYP enzymes

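### The patient diary permits vitamin E supplements up to 100% of the daily allowance, while the protocol body permits none

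*Combined protocol and SAP*

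**What the plan says.** Three places in the protocol body address supplemental vitamin E, and none gives a dose threshold.

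- Section 3.29j excludes a patient who is "Not willing to discontinue use of supplemental vitamin E".
- Section 7.1, under Placebo or Selumetinib, says "Patients should not take any supplemental vitamin E".
- Section 15.16 says "The concomitant intake of supplemental vitamin E should be avoided in all subjects receiving selumetinib".

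Section 7.1 gives the reason. The capsules use a form of vitamin E as an excipient: "The maximum daily dose of vitamin E that a study subject may receive from selumetinib/placebo is approximately 261.6 mg/day". It adds that "High doses of vitamin E have been reported to cause bleeding and interrupt blood coagulation processes". Section 15.16 notes that "High vitamin E doses may potentiate the anticoagulant activity of warfarin". Section 3.29j gives no reason. Section 15.12 shows that the placebo carries vitamin E too, "with the absent drug substance being replaced by Vitamin E polyethylene glycol succinate".

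The diary in Appendix II, in its instructions to the patient, reads differently: "Do not take vitamin E or multivitamin supplements that provide a total daily dose in excess of 100% of the recommended daily allowance", the allowance being that for vitamin E.

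**The concern.** The diary is addressed to the patient and is in use throughout dosing. It sets a ceiling where the protocol body sets a prohibition, and nothing in the documents reconciles the two or creates an exception up to one daily allowance.

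The protocol reasons that the capsules already carry a substantial vitamin E load, so none should be added. The diary's limit, as worded, counts only what supplements provide and does not mention the capsules. The diary does not tell anyone to take vitamin E. However, a patient who follows it faithfully could depart from Section 7.1 without knowing it. What is at stake is adherence to a safety rule about bleeding, in both arms.

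**Working it through.** There is no figure in the plan to reproduce. The check is a comparison of texts, followed by a rough sizing.

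**1. Amount of supplemental vitamin E allowed**

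| Place | Amount allowed |
|---|---|
| Section 3.29j | none (patient must be willing to stop) |
| Section 7.1 | none |
| Section 15.16 | none (to be avoided) |
| Appendix II diary | up to 100% of the daily allowance |

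**2. Two readings of the diary sentence**

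- *The limit covers both products.* A vitamin E supplement at or below the allowance is left open. This contradicts Section 7.1 directly.
- *The limit covers only multivitamins.* Vitamin E supplements are barred outright, which agrees with the protocol body, but a multivitamin containing vitamin E at or below the allowance is left open. The protocol body does not name multivitamins. The conflict here rests on Section 7.1's ban on any supplemental vitamin E reaching the vitamin E inside a multivitamin. That is the natural meaning, and the diary itself treats multivitamins as a source of vitamin E.

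The mismatch is present on both readings. It is explicit on the first and depends on that one inference on the second.

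**3. Size**

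Inputs:

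- Capsule load: 261.6 mg/day at most (Section 7.1).
- Duration: at most 8 weeks including interruptions (Section 4.0 footnote 1; Section 7.1).
- Daily allowance A: not in the documents; assumed to be 10 to 30 mg/day.
- Capsule and supplement milligrams are assumed to be comparable.

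Total at the diary limit = 261.6 + A:

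- A = 10: 261.6 + 10 = 271.6 mg/day; 10 / 261.6 = +3.8%.
- A = 30: 261.6 + 30 = 291.6 mg/day; 30 / 261.6 = +11.5%.

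Because 261.6 mg/day is a maximum, a patient receiving less from the capsules would have a larger percentage increase but a smaller total.

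**The case against.** The strongest reply is that the consequence is close to nil. The hazard is described for high doses, the diary allows at most one daily allowance, and treatment is planned for about 4 weeks and capped at 8. This stands, and it is why the point is minor.

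Second, the protocol's wording is softer than an absolute ban. Section 7.1 introduces its list as recommendations to be followed, Section 15.16 speaks of avoidance, and Section 3.29j tests willingness at entry rather than conduct on treatment. This is fair, but none of the three states a threshold, so the mismatch with the diary remains.

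Third, other provisions limit exposure:

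- Enrolled patients have already been screened for willingness to stop vitamin E.
- Section 7.1 discourages adding concomitant medications and asks for more frequent INR or anticoagulation checks in warfarin users.
- Section 15.199d has staff review concomitant medications.
- Appendix III tells patients to avoid vitamins that contain iodine, and to leave them out if in doubt, during the low-iodine diet.
- Section 4.0 footnote 11 lets compliance be recorded in the medical record instead of the diary.

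These lower the chance of harm. Beyond the entry screen, however, none states a vitamin E rule to the patient, and the diet sheet concerns iodine over a short period only. The consent form was not available for review, so what patients are told elsewhere is unknown.

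Finally, the multivitamin point requires an inference, as set out in the working. The inference is reasonable, and the plainer reading of the diary does not need it.

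**Conclusion.** The concern holds. The diary gives patients a looser vitamin E rule than the protocol body, and nothing in the available documents reconciles them. It is an internal inconsistency in a patient instruction and a minor point. Under the assumed allowance of 10 to 30 mg/day, the extra intake is 3.8% to 11.5% above the maximum capsule load, for at most 8 weeks, in either arm. The added bleeding risk is probably small, cannot be estimated from the documents, and is of most interest in patients on warfarin. The primary endpoint, sample size, power and analysis are unaffected.

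**What to change.** Leave Sections 3.29j, 7.1 and 15.16 as the governing text. Replace the diary sentence with:

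> Do not take any vitamin E supplement, or any multivitamin that contains vitamin E, while taking study capsules; the capsules already contain vitamin E.

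The cost is a diary reprint and IRB notification. Patients who use an ordinary multivitamin would have to stop it, or switch to one without vitamin E, for up to 8 weeks. On the natural reading of Section 7.1, that is already expected of them. The consent form should be checked for the same wording at the same time.
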